## 22.3 Meal and Liquids Log

Please indicate the type and value of the food and liquids you consumed during the preparation days:

		Day -1 (Day prior to procedure)	Day of Procedure Nothing Per Oral 3 Hours Prior to Colonoscopy
Breakfast	Food		
	Volume and Type of Clear Liquids		
Lunch	Food		
	Volume and Type of Clear Liquids		After the procedure please return to your normal daily diet
Dinner	Food		
	Volume and Type of Clear Liquids		

Document title:  Optimizing the Preparation Regime Prior to Colonoscopy Procedure with Pure-Vu System	Document No.  CL00042	Version  1.0	Page 51 of 61
---	------------------------------------	---------------------------	------------------

## 22.5 Bowel Movements Log

Day -1 (Day prior to procedure)	Day of Procedure
Time of BM:  Please Circle: Formed or Liquid	Time of BM:  Please Circle: Formed or Liquid
Time of BM:  Please Circle: Formed or Liquid	Time of BM:  Please Circle: Formed or Liquid
Time of BM:  Please Circle: Formed or Liquid	Time of BM:  Please Circle: Formed or Liquid
Time of BM:  Please Circle: Formed or Liquid	Time of BM:  Please Circle: Formed or Liquid
Time of BM:  Please Circle: Formed or Liquid	Time of BM:  Please Circle: Formed or Liquid
Time of BM:  Please Circle: Formed or Liquid	Time of BM:  Please Circle: Formed or Liquid
Time of BM:  Please Circle: Formed or Liquid	Time of BM:  Please Circle: Formed or Liquid
Time of BM:  Please Circle: Formed or Liquid	Time of BM:  Please Circle: Formed or Liquid
Time of BM:  Please Circle: Formed or Liquid	Time of BM:  Please Circle: Formed or Liquid
Time of BM:  Please Circle: Formed or Liquid	Time of BM:  Please Circle: Formed or Liquid

Document title:	Document No.	Version	Page 52 of 61
Optimizing the Preparation Regime Prior to Colonoscopy Procedure with Pure-Vu System	CL00042	1.0	

### 23.0 Appendix E – Case Report Form (filled-in by the patient)

**Pure-Vu™**  
**Patient Satisfaction Questionnaire**

**Procedure Date / Patient ID Number:** \_\_\_\_\_ / \_\_\_\_\_

**Physician Name:** \_\_\_\_\_

*The patient will answer the following questions prior the colonoscopy procedure*

Question #1	Yes	No
Was this your first colonoscopy?		

Question #2	Very Easy	Easy	Tolerable	Difficult	Very Difficult
How tolerable did you find the low fiber diet in this bowel preparation process?					
How tolerable did you find the bowel cleansing purgative in this bowel preparation process?					
How disruptive was the bowel preparation process to your normal activities?					

Question #3
If you could change two things in the bowel preparation process, what would they be?
1
2

CONFIDENTIAL

Document title:  Optimizing the Preparation Regime Prior to Colonoscopy Procedure with Pure-Vu System	Document No.  CL00042	Version  1.0	Page 53 of 61
---	------------------------------------	---------------------------	------------------

***The patient will answer the following questions after the colonoscopy procedure during the follow up phone call (will be filled by the site study coordinator)***

Question #4	Yes	No
Based upon your experience with Pure-Vu, would you recommend Pure-Vu to your friends and family members who need a colonoscopy?		

Please explain why:

---

---

Question #5	Yes	No
Would you request Pure-Vu for your next colonoscopy?		

Question #6	Yes	No
Would you request Pure Vu again for your next colonoscopy if it cost \$300?		

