### **Patient Satisfaction**

Patient satisfaction will be evaluated by a questionnaire (Appendix E). The patient will be asked to fill-in a questionnaire and include their feedback on the procedure including specific aspects related to the preparation regime.

Patient satisfaction will be summarized in a table via descriptive statistics by data type. Chi-square or Fisher's exact test, as appropriate, will be performed in order to compare the patient satisfaction between the two study arms.

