**If this was not your first colonoscopy, please answer questions 7 - 11.**  
**Please answer question 7-10 prior the colonoscopy procedure. Please add any additional comments at the end of the questionnaire**

Question #7	Yes	No
Was this preparation different from your previous preparation?		

If the preparation was different, please explain how and / or why:

---

---

Document title:  Optimizing the Preparation Regime Prior to Colonoscopy Procedure with Pure-Vu System	Document No.  CL00042	Version  1.0	Page 54 of 61
---	-----------------------------	--------------------	------------------

Question #8	This Pure-Vu prep was more tolerable than before	This Pure-Vu prep was about the same as before	This Pure-Vu prep was less tolerable than before
How would you compare the tolerability of the preparation with Pure-Vu to your previous colonoscopy?			

If the tolerability of this preparation was different, please explain how and / or why:

---

---

Question #9	Pure-Vu diet was better than before	Pure-Vu diet was about the same as before	Pure-Vu diet was worse than before
How would you compare the dietary restrictions with Pure-Vu to your previous colonoscopy?			

If your dietary experience was different, please explain how and / or why:

---

---

Document title:  Optimizing the Preparation Regime Prior to Colonoscopy Procedure with Pure-Vu System	Document No.  CL00042	Version  1.0	Page 55 of 61
---	-----------------------------	--------------------	------------------

Question #10	Pure-Vu experience was less disruptive than before	Pure-Vu experience was about the same as before	Pure-Vu experience was more disruptive than before
How would you compare the disruption to your daily activities with Pure-Vu to your previous colonoscopy experience?			

If the disruption to your daily activities was different, please explain how and / or why:

---

---

***The patient will answer the following question after the colonoscopy procedure during the follow up phone call (will be filled by the site study coordinator)***

Question #11	Pure-Vu experience was better than before	Pure-Vu experience was about the same as before	Pure-Vu experience was worse than before
How would you compare your overall Pure-Vu experience to your previous colonoscopy experience?			

If your experience was different, please explain how and / or why:

---

---

CONFIDENTIAL

Document title:	Document No.	Version	Page 56 of 61

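### The disruption item in the patient questionnaire is answered on an ease/difficulty scale that does not fit its question, which may dilute a planned between-arm comparison

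*Protocol*

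**What the plan says.** Appendix E, Question #2 prints one header, "Very Easy Easy Tolerable Difficult Very Difficult", above three rows. The first two ask about tolerability, of the low-fibre diet and of the purgative; the latter reads "How tolerable did you find the bowel cleansing purgative in this bowel preparation process". The third row changes the subject: "How disruptive was the bowel preparation process to your normal activities". It has no answer labels of its own.

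The form asks about disruption once more, in Question #10: "How would you compare the disruption to your daily activities with Pure-Vu to your previous colonoscopy experience". There the answers match the question, for example "Pure-Vu experience was less disruptive than before". That block is restricted, however: "If this was not your first colonoscopy, please answer questions 7 - 11". It is also relative to the earlier colonoscopy, and the instruction on timing is "Please answer question 7-10 prior the colonoscopy procedure".

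Section 12.4 (Patient Satisfaction) takes its data from Appendix E and states that a Chi-square or Fisher's exact test "will be performed in order to compare the patient satisfaction between the two study arms". Section 8.2 lists patient satisfaction as a secondary objective. It is not among the secondary endpoints in section 9.2 or the synopsis.

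**The concern.** A question about degree of disruption needs answers that express a degree of disruption. Here the patient must translate. *Very Easy* has to stand for not disruptive, *Very Difficult* for very disruptive, and *Tolerable* for something in between. A patient may instead rate how hard the preparation was in general, which repeats the two rows above, or may match the boxes to the stem in some other way.

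At stake is the one item, answered by every patient, that records what each preparation did to normal activities. It is compared between two preparations that differ in volume. Error made when the box is ticked cannot be removed later, because no analysis rule can recover what the patient meant. For that reason this is not a matter that can be left to a statistical analysis plan: the protocol itself fixes the form.

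**Working it through.** **No plan figure to reproduce.** The protocol gives no effect size, significance level, power or expected answer distribution for this item. Section 12.1 says the sample size has no statistical basis. The check is therefore of wording first, followed by an illustration on assumed values.

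**Step 1: does the scale fit each row?**

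| Item | Asks about | Answers offered | Fit | Who answers |
|---|---|---|---|---|
| Q2, row 1 | tolerability of diet | ease to difficulty | reasonable | all |
| Q2, row 2 | tolerability of purgative | ease to difficulty | reasonable | all |
| Q2, row 3 | disruption of activities | ease to difficulty | none of the five states a degree of disruption | all |
| Q10 | disruption against last time | less / same / more disruptive | matched | prior colonoscopy only |

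Row 3 is the only mismatch, and it is the only disruption item with full coverage.

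**Step 2: what can misreading do?** Collapse the answers to favourable or unfavourable. Let the true unfavourable proportions be pA and pB, and let a share m of patients in each arm read the scale in reverse. Then

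- observed p = p(1 − m) + (1 − p)m
- observed difference = (pA − pB)(1 − 2m)

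For any m below 0.5 the factor is positive, so the direction is kept and the size is reduced. If the shares differ (mA and mB) and the true proportions are equal at p, the observed difference is (mA − mB)(1 − 2p), which need not be zero. The dilution result therefore depends on misreading being equally common in both arms.

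**Step 3: illustration.** Every input here is an assumption except the ceiling of 100 patients. Take 50 per arm, two-sided alpha 0.05, and true unfavourable rates of 45% and 20%. With d the observed difference and p̄ the mean of the two observed proportions,

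- power = Φ[(d − 1.96·se0)/se1]
- se0 = √(p̄(1 − p̄)·2/n)
- se1 = √((pA(1 − pA) + pB(1 − pB))/n)

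At m = 0: d = 0.25, p̄ = 0.325, se0 = 0.0937, se1 = 0.0903, so power = Φ(0.74), about 77%.

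At m = 10%: pA becomes 0.45·0.90 + 0.55·0.10 = 0.46 and pB becomes 0.20·0.90 + 0.80·0.10 = 0.26, so d = 0.20.

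| m (assumed) | Factor 1 − 2m | Difference, 45% v 20% | Power, 50/arm | Power, 45/arm | Difference, 40% v 25% | Power, 50/arm |
|---|---|---|---|---|---|---|
| 0 | 1.0 | 25 points | 77% | 72% | 15 points | 36% |
| 5% | 0.9 | 22.5 points | 66% | 62% | 13.5 points | 29% |
| 10% | 0.8 | 20 points | 55% | 51% | 12 points | 24% |
| 20% | 0.6 | 15 points | 33% | 31% | 9 points | 15% |

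The 45-per-arm column corresponds to three sites with 15 patients per arm each. The table shows how sensitive the comparison would be if patients reversed the scale. It is no evidence that they would.

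**The case against.** The strongest reply is that this is a copy-editing slip with little practical effect. The three rows share a header that runs from favourable to unfavourable. A patient who has just answered two tolerability rows would naturally take *Very Difficult* as the bad end. Complete reversal, which drives the table above, is the least plausible way to misread the row, and nothing in the protocol suggests how often it would happen. This stands, and it is why no size can be claimed.

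A reader might also infer that this is a key burden comparison. The protocol does not support that. Satisfaction is absent from the endpoint lists. The stated reasons for a smaller preparation are palatability and volume (section 5.1), discomfort and adverse events (7.2), and compliance and discomfort (7.4). The two tolerability rows speak to those reasons and fit their scale. Question #3 adds free text from all patients, and Questions #8 to #10 add graded items from those with a previous colonoscopy. These soften the problem. They do not remove it, since none gives a usable disruption grade for every patient.

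A further tempting reading is that Question #10 is asked too early, because its answers refer to the Pure-Vu experience before the procedure has taken place. Its stem concerns disruption to daily activities, it sits with other pre-procedure items on preparation and diet, and Question #11 collects the overall experience afterwards. The timing is coherent. Only the word *experience* in the answer boxes is loose.

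**Conclusion.** The mismatch is real and visible on the form: none of the five answers to the disruption row states a degree of disruption. The supported conclusion is that the answers are ambiguous and may dilute the between-arm comparison on this one item.

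The documents do not support saying that the item cannot be read reliably, or that the satisfaction comparison as a whole is compromised. Nor do they support a fixed percentage loss, since the misreading rate is unknown. The expectation of dilution, and not of a tilt towards one preparation, assumes equal misreading in both arms. Both arms use the same form, but the study is open-label, so this remains an assumption. No figure in the protocol changes. Priority is low.

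**What to change.** Give the third row of Question #2 its own five answers: *Not at all*, *Slightly*, *Moderately*, *Very* and *Extremely disruptive*. Keep them in the favourable-to-unfavourable order of the other rows, so that the page still reads in one direction and the planned tests need no change.

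Optionally, refer to the preparation in place of the Pure-Vu experience in the Question #10 answers. Keep that question before the procedure. Moving it to the follow-up call would mix in disruption from the procedure and recovery, which is a different quantity.

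The cost is a minor change to the questionnaire appendix, on one page, or two if Question #10 is also reworded. It needs sponsor and IRB approval under sections 14.2 and 14.4, best obtained before the first patient is enrolled so that all patients answer the same form. No sample size, endpoint or study procedure is affected.

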**If this was not your first colonoscopy, please answer questions 7 - 11.**  
**Please answer question 7-10 prior the colonoscopy procedure. Please add any additional comments at the end of the questionnaire**

Question #7	Yes	No
Was this preparation different from your previous preparation?		

If the preparation was different, please explain how and / or why:

---

---

Document title:  Optimizing the Preparation Regime Prior to Colonoscopy Procedure with Pure-Vu System	Document No.  CL00042	Version  1.0	Page 54 of 61
---	-----------------------------	--------------------	------------------

Question #8	This Pure-Vu prep was more tolerable than before	This Pure-Vu prep was about the same as before	This Pure-Vu prep was less tolerable than before
How would you compare the tolerability of the preparation with Pure-Vu to your previous colonoscopy?			

If the tolerability of this preparation was different, please explain how and / or why:

---

---

Question #9	Pure-Vu diet was better than before	Pure-Vu diet was about the same as before	Pure-Vu diet was worse than before
How would you compare the dietary restrictions with Pure-Vu to your previous colonoscopy?			

If your dietary experience was different, please explain how and / or why:

---

---

Document title:  Optimizing the Preparation Regime Prior to Colonoscopy Procedure with Pure-Vu System	Document No.  CL00042	Version  1.0	Page 55 of 61
---	-----------------------------	--------------------	------------------

Question #10	Pure-Vu experience was less disruptive than before	Pure-Vu experience was about the same as before	Pure-Vu experience was more disruptive than before
How would you compare the disruption to your daily activities with Pure-Vu to your previous colonoscopy experience?			

If the disruption to your daily activities was different, please explain how and / or why:

---

---

***The patient will answer the following question after the colonoscopy procedure during the follow up phone call (will be filled by the site study coordinator)***

Question #11	Pure-Vu experience was better than before	Pure-Vu experience was about the same as before	Pure-Vu experience was worse than before
How would you compare your overall Pure-Vu experience to your previous colonoscopy experience?			

If your experience was different, please explain how and / or why:

---

---

CONFIDENTIAL

Document title:	Document No.	Version	Page 56 of 61
Optimizing the Preparation Regime Prior to Colonoscopy Procedure with Pure-Vu System	CL00042	1.0	

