### 8.2 Secondary objectives:

- To evaluate the safety related to the Pure-Vu System in both study arms.
- To evaluate the time to reach the Cecum in Pure-Vu procedures in both study arms.
- To evaluate the total procedure time with Pure-Vu in both study arms.
- To evaluate the cecal intubation rate with Pure-Vu in both study arms.
- To evaluate patients' satisfaction with Pure-Vu procedure in both study arms.
- To evaluate Pure-Vu user satisfaction with Pure-Vu procedure in both study arms.

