## 19.0 Appendixes A: Study Design and Schedule of Assessment

Visit	Visit 1	Colon Preparation	Visit 2	Contact
Days	>-5 days	-1 to 0 days	0	48 hours
Informed Consent*	X			
Eligibility assessment (medical records, BMI, etc.)	X			
Randomization	X			
Colon Preparation Instructions	X			
Medical History, Concomitant Medications, Demographic details	X			
Diaries	X (providing)	X (by the patients)		
Patients' satisfaction questionnaire	X (providing)	X	X	
Bowel Preparation		X (by the patients)		
Colonoscopy Procedure			X	
Follow Up			X	X
Adverse Events Reporting			X	

Document title:	Document No.	Version	Page 45 of 61
Optimizing the Preparation Regime Prior to Colonoscopy Procedure with Pure-Vu System	CL00042	1.0	

[figure not shown]

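### Question 10 of the patient questionnaire is answered before the procedure, but its answers rate the Pure-Vu experience against a whole earlier colonoscopy

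*Protocol*

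**What the plan says.** Section 8.2 lists this secondary objective: "To evaluate patients' satisfaction with Pure-Vu procedure in both study arms". Section 12.4 refers to the questionnaire in Appendix E and plans descriptive summaries and a chi-square or Fisher's exact test between the two arms.

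Appendix E has 11 numbered questions. The last five are for patients who have had a colonoscopy before: "If this was not your first colonoscopy, please answer questions 7 - 11". Their timing follows at once: "Please answer question 7-10 prior the colonoscopy procedure". Question 10 reads "How would you compare the disruption to your daily activities with Pure-Vu to your previous colonoscopy experience", and its first answer option is "Pure-Vu experience was less disruptive than before".

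The form gives a different time for Questions 4 to 6: "The patient will answer the following questions after the colonoscopy procedure during the follow up phone call". It repeats that instruction for Question 11. Section 11.1.5, under post-examination follow-up, describes the phone contact and then says that questions on satisfaction with the Pure-Vu procedure will be completed.

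Appendix A has a row headed "Patients' satisfaction questionnaire". It is marked at Visit 1 (when the form is handed out), at Colon Preparation and at Visit 2. The Contact column is blank.

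**The concern.** Pure-Vu is used during the colonoscopy. A patient who completes Question 10 beforehand has followed the diet and taken the purgative but has no experience of the device, the procedure day as a whole or the recovery. The earlier colonoscopy that serves as comparator includes all of these. The answer options nevertheless use the past tense and name the Pure-Vu experience.

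At stake is what a table of Question 10 answers means. A reader of the results would take it as patients' judgement of Pure-Vu against their last colonoscopy, when it records a judgement made before Pure-Vu was used. Leaving the procedure and recovery out of one side only would plausibly push answers towards less disruption. Answers given at the wrong time cannot be corrected afterwards.

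A smaller matter is that the schedule table and the form disagree on whether the questionnaire is used at the follow-up contact.

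**Working it through.** No arithmetic beyond counting applies, and the protocol states no figure to reproduce. The check is to set the texts side by side.

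**Timing of the 11 questions in Appendix E**

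| Questions | When answered | By whom |
|---|---|---|
| 1–3 | before the procedure | all patients |
| 4–6 | follow-up call | all patients |
| 7–10 | before the procedure | earlier colonoscopy only |
| 11 | follow-up call | earlier colonoscopy only |

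Before the procedure: 3 + 4 = 7. At the call: 3 + 1 = 4. Total: 7 + 4 = 11.

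**Wording against timing in the repeat-colonoscopy block**

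- Question 7 asks whether the preparation differed from the last one. This can be answered beforehand.
- Question 8 compares tolerability, and its answers are limited to the preparation. This fits the timing.
- Question 9 compares dietary restrictions, and its answers are limited to the diet. This fits the timing.
- Question 10 compares disruption to daily activities. Its answers rate the Pure-Vu experience, and its comparator is the previous colonoscopy experience. Neither is limited to the preparation.
- Question 11 compares overall experience. Its answers also rate the Pure-Vu experience, and it is asked after the procedure.

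Question 10 thus uses the answer wording of the post-procedure item at the time set for the preparation items. The form does have wording for disruption by the preparation alone. The third item of Question 2 asks "How disruptive was the bowel preparation process to your normal activities", is put to all patients and is correctly timed. Question 10 does not use that wording.

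**Effect on the two planned analyses (section 12.4)**

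- *Descriptive summary.* The current side covers the preparation only, while the comparator covers preparation, procedure and recovery. The two sides do not match, so the summary does not measure what its labels say. The protocol gives no figure from which to size the distortion, and none is assumed here.
- *Between-arm test.* Timing and wording are the same for Prep A and Prep B. Having had an earlier colonoscopy is settled before randomisation, so restricting the item to those patients does not break the randomised comparison. The mismatch alone does not bias the test.

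**Schedule.** Appendix E places 4 of 11 questions at the call, and section 11.1.5 agrees. The questionnaire row of Appendix A has no mark at Contact. The Follow Up row is marked there, so the call itself is scheduled.

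**The case against.** The best defence of Question 10 is that its stem is about disruption to daily activities, which the days of diet and the purgative largely cause. It also closes a block in which Pure-Vu serves as a label for the regimen, as in Questions 8 and 9, while the overall experience is left to Question 11. Much of this stands: the item is partly answerable before the procedure, and disruption by the preparation is separately captured in Question 2. What remains is that the comparator is the whole previous experience and the answers name the Pure-Vu experience without limiting it to the preparation.

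A reader might infer from Appendix A that the post-procedure satisfaction items will be missed or asked at the wrong visit, so that the secondary objective is lost. The documents do not support that. The form prints the call timing directly above Questions 4 to 6 and again above Question 11, has the site coordinator fill them in, and agrees with section 11.1.5. Appendix A also leaves adverse event reporting unmarked at Contact, although sections 9.0 and 11.1.5 capture events at the call. The table therefore looks like an incomplete summary, and marks may also have been lost when the PDF was read.

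A reader might also infer that the early timing biases the comparison of the two preparations. It does not, because the timing is common to both arms.

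**Conclusion.** The point holds for Question 10. As written, its answers cannot be reported as a comparison of Pure-Vu with previous colonoscopy. The scope is one question of 11, in the subset of patients with an earlier colonoscopy, whose number the protocol does not give. Only the descriptive reading is affected. A tilt towards less disruption is plausible but rests on the assumption that the procedure and recovery add to disruption; its size is unknown.

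The blank in Appendix A is an inconsistency with the form and section 11.1.5, to be reconciled as a minor matter. The primary endpoint is untouched. Patient satisfaction is an objective in section 8.2 but does not appear in the endpoint list of section 9.2, and the study is an unpowered pilot, which keeps the weight of this point modest. It is still worth correcting before enrolment.

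**What to change.** Choose one of two changes to Question 10:

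1. Keep it before the procedure, and reword stem and answers so that they compare the disruption caused by this bowel preparation with that caused by the previous bowel preparation.
2. Keep the wording, and move the item to the follow-up-call block with Question 11.

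The first keeps the item with the preparation questions and isolates what the two arms differ in. The second covers the full episode on both sides. Either is sound if the results are labelled to match. With the second, the instruction above Questions 7 to 10 must be shortened to 7 to 9.

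In Appendix A, mark the questionnaire row at Contact, and state which questions belong to which column: 1–3 and 7–9 before the procedure, 4–6 and 11 at Contact, and Question 10 according to the option chosen.

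The cost is one edited or moved item and one table mark with its labels. The call is already planned and the coordinator already completes the form during it, so no visit or extra contact is added.
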